8 DISCONTINUATION FROM THE STUDY

Participants discontinued from a study will be reimbursed [REDACTED] [REDACTED] (including the initial screening visit). A participant's study participation may be discontinued at any time if, in the opinion of the sponsor or the investigator it is in the

best interest of the participant. All discontinuations will be fully documented on the appropriate study forms and the Discontinuation Form will be completed. The following is a list of possible reasons for discontinuation from the study:

- Screening failure: Participants will be discontinued if they do not meet the inclusion and exclusion criteria outlined in section 4.6.2.
- Unacceptable performance with products to be used in study: Participants may be discontinued if they are unable to achieve acceptable comfort and /or vision with the study products.
- Positive slit lamp finding: Participants may be temporarily or permanently discontinued from the study depending on the severity of the condition and on the judgement of the investigator.
- Adverse event: If a participant experiences an adverse event during the study they may be discontinued based on the clinical judgement of the investigator.
- Symptoms: If the participant has persistent symptoms they may be discontinued based on the clinical judgement of the investigator.
- Disinterest, relocation or illness: The participant may choose to discontinue due to reasons within or beyond their control.
- Violation of protocol or non-compliance: The participant will be discontinued if they are unable or unwilling to follow the protocol specified visit schedules and/or study procedures.
- Instillation of topical ocular medication: The participant will be discontinued if they elect to use a topical ocular medication during the study unless that topical ocular medication is prescribed for a limited duration (less than two weeks) to treat a transient condition; in this case the participant may remain an active participant (at the discretion of the investigator) after stopping topical ocular medication following resolution of the ocular condition).
- Lost to follow-up: The participant will be discontinued if they cannot be contacted and do not return for a final exit visit, and if the investigator has made a reasonable effort to contact the participant for a final study visit.
- Premature termination of the study by the sponsor, the CCLR or the Office of Research Ethics at the University of Waterloo.

A discontinuation form (Appendix 13) will be completed, which requires the signatures of both the participant and the investigator except where the participant is lost to follow-up in which case only the signature of the investigator is required.

9 DEVICE MALFUNCTIONS

A device malfunction means the failure of the device to meet its performance specification or otherwise perform as intended. *Any defective lens that is likely to cause or contribute to a Serious Adverse Event should be reported to the Principal Investigator and the sponsor **within 24 hours** of the investigator becoming aware of the malfunction. The ORE would also be notified within 24 hours of any device malfunction that may contribute to a Serious Adverse Event.*

Other defective lenses should be reported to the Sponsor as soon as possible (usually in weekly study updates to the Sponsor).

This clinical study will also ascertain satisfaction or preference with subjective attributes such as comfort, vision, or lens handling. Responses to these subjective questionnaires will not be considered as complaints or device malfunctions.

10 STUDY COMPLETION AND REMUNERATION

At the last scheduled protocol visit a study completion form (Appendix 25) will be completed, which requires the signatures of both the participant and the investigator. The participants will also be provided with a letter of appreciation (Appendix 16).

Once their involvement in the study is complete, participants will be informed about receiving feedback following study completion in the Letter of Appreciation (Appendix 16).

Participant remuneration will be [REDACTED] (including the initial screening visit). Full details are given in the information consent letter (Appendix 1).

11 STATISTICAL ANALYSIS AND DATA MANAGEMENT

11.1 SAMPLE SIZE CALCULATION

The maximum sample size will be 52. For a two-sided paired t-test with an alpha of 0.05 and a power goal of 80%, this will allow an effect size as small as 0.28 to be detected. This sample size will give approximately 80% confidence to detect a difference of 5 points in comfort ratings.

Table 4 shows the sample size determination for a difference between two means in comfort scores. Sample sizes with 80% power are shown at two different alpha levels (alpha = 0.05 and alpha = 0.10). Assuming a standard deviation of 12.6 points, a sample size of 52 participants provides 80% power to detect a trend in difference of comfort scores between 5 points on a 100-point scale.

Table 4: Sample size calculation

Mean individual	Mean individual	Sample size	Sample size
-----------------	-----------------	-------------	-------------

difference in score	standard deviation	(p = 0.05)	(p = 0.10)
5	12.6	52	41
7	17.6	52	41

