4.6 STUDY POPULATION

4.6.1 NUMBER OF PARTICIPANTS

Up to 52 participants will be dispensed / randomized with study products, with a target of 45 completing the study. Participants will be recruited using CCLR records and advertising approved by the UW Office of Research Ethics (Appendices 2, 3a, and 3b). Each participant will be given a unique ID number. Additionally, all participants must meet the study inclusion and none of the exclusion criteria listed below.

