4.8 SCHEDULED AND UNSCHEDULED VISITS

This study has a total of 4 scheduled study visits, including:

- Visit 1: Baseline includes screening and dispense of lens pair #1,
- Visit 2: 1-week follow-up visit of lens pair #1 after 7-10 days and dispense of lens pair #2;
- Visit 3: 1-week follow-up visit of lens pair #2 after 7-10 days and dispense of lens pair #3;
- Visit 4: 1-week follow-up visit of lens pair #3 after 7-10 days and study exit.

A scheduled follow-up visit may only take place when the participant attends wearing the study lenses. If this is not the case and the participant is not experiencing any problems with the lenses, the appointment will be rescheduled, ideally within the visit window.

Visits that fall outside of the specified visit windows will be designated as protocol deviations and at the end of the study the data collected will be assessed for its suitability to be included in the analysis population.

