11.2 STATISTICAL ANALYSIS

All data will be analyzed by the CCLR at the University of Waterloo. Summary statistics will be produced (e.g. mean, standard deviation). Data analysis will be conducted using Statistica and / or SPSS. Descriptive statistics will be provided on information regarding baseline variables (age, gender, refractive error distribution, etc.). Analysis of variables will be conducted separately on each eye, and data will not be pooled. A Binomial test will be used to analyze the results for the count data of subjective preferences. The number of “no preference” will be evenly distributed to the two options on the basis they would be equally likely to choose either.

Table 5 lists the primary outcome variables and anticipated statistical procedures.

Table 5: Outcome variables and anticipated statistical procedures

Variable	Analysis	Statistical test
Analogue scales/Numeric scales/Preference scales/VA Lens parameters, Biomicroscopy (continuous variables)	Effect of lens type	RMANOVA/MANOVA/ Friedman /Wilcoxon matched pairs test Tukey HSD post hocs Paired t-test Chi-square test
Biomicroscopy (ordinal variables)	Effect of lens type	Friedman Wilcoxon matched pairs test
Analogue scales/Numeric scales/Lens parameters, Biomicroscopy (continuous)	Relationship between slit lamp findings and analogue scales	Pearson correlation - r
Biomicroscopy (ordinal variables)	Relationship between slit lamp findings and analogue scales	Spearman correlation - rho

The critical alpha level for statistical significance will be set at $p \leq 0.05$, with no adjustments for multiple comparisons.

All participants who were evaluated will be used in the analysis. In the event of missing data, individual data points will be excluded in the analysis and not extrapolated from the collected data.

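### Section 11.1 gives 0.28 as the detectable effect size with 52 participants; read as a paired effect size its own inputs and Table 4 give 0.40, and power at the 45-completer target (74%) is not stated

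*Combined protocol and SAP*

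**What the plan says.** Section 11.1 opens with "The maximum sample size will be 52". It names a two-sided paired t-test at alpha 0.05 with an 80% power goal, and concludes that "this will allow an effect size as small as 0.28 to be detected". It does not define effect size, and it gives no single-lens SD and no within-person correlation.

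The next paragraph assumes an SD of 12.6 points and says that "a sample size of 52 participants provides 80% power" for a 5-point difference in comfort on a 100-point scale. Table 4 has two rows: a difference of 5 with SD 12.6, and a difference of 7 with SD 17.6. Both rows give 52 participants at alpha 0.05 and 41 at alpha 0.10.

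Section 4.6.1 says: "Up to 52 participants will be dispensed / randomized with study products, with a target of 45 completing the study". Two other provisions affect how many pairs reach a comparison. For visits outside the window, section 4.8 says that "the data collected will be assessed for its suitability to be included in the analysis population". Section 11.2 says: "In the event of missing data, individual data points will be excluded in the analysis", with no imputation.

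**The concern.** The test, alpha, power and sample size in section 11.1 together fix the smallest paired effect size that can be detected. The stated 0.28 is well below what they give, and it disagrees with the table beneath it. A reader who takes 0.28 as a paired effect size would expect 80% power in a situation where the trial has about an even chance of a significant result. Table 4 covers comfort only, while dryness and visual quality are also primary outcomes (section 2). The standardised figure is therefore the one a reader would carry over to those ratings.

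The second point is that the 80% power needs all 52 participants to supply an analysable pair. Since 52 is the ceiling on randomization and 45 is the completion target, the plan expects fewer complete data sets than its power statement uses. It gives no power for that case.

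**Working it through.** **Inputs.** From section 11.1: two-sided paired t-test, alpha 0.05 (also 0.10 in Table 4), power 80%, n = 52, differences and SDs of 5 and 12.6, and 7 and 17.6. From section 4.6.1: 45 completers.

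**Formula.** Let d = mean difference / SD of within-participant differences. With n pairs the test statistic follows a noncentral t distribution with n − 1 degrees of freedom and noncentrality d√n. Power is the probability that it falls beyond ± the critical t value.

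**Step 1: reproduce Table 4.** The ratios are 5/12.6 = 0.3968 and 7/17.6 = 0.3977.

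| Row | Alpha | Smallest n with power ≥ 80% | Table 4 |
|---|---|---|---|
| 5 / 12.6 | 0.05 | 52 (power 80.2%) | 52 |
| 5 / 12.6 | 0.10 | 41 (power 80.3%) | 41 |
| 7 / 17.6 | 0.05 | 52 (power 80.3%) | 52 |
| 7 / 17.6 | 0.10 | 41 (power 80.5%) | 41 |

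All four entries reproduce when the tabulated SD is the SD of differences. For the first row the noncentrality is 0.3968 × √52 = 2.862, against a critical value of 2.008.

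**Step 2: detectable effect size with 52 pairs.** Solving for 80% power gives d = 0.396 at alpha 0.05, which is 0.396 × 12.6 = 4.99 points. At alpha 0.10 it is 0.349. Neither is 0.28.

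**Step 3: what 0.28 would mean as a paired effect size.** With 52 pairs the noncentrality is 0.28 × √52 = 2.019, which gives 50.8% power at alpha 0.05 and 63.6% at alpha 0.10. At alpha 0.05, 102 pairs give 79.98% and 103 give 80.4%, so 103 are needed.

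**Step 4: where 0.28 might come from.** Several routes round to it:
- Single-lens SD. The SD of differences equals the single-lens SD × √(2(1 − r)). Setting 0.28/√(2(1 − r)) = 0.396 gives r = 0.75, which is the same as 0.396/√2 = 0.280.
- A two-level repeated-measures ANOVA effect size f with zero correlation: 0.280 at n = 52.
- Row 1 difference over row 2 SD: 5/17.6 = 0.284.
- 104 eyes treated as pairs: 0.277. However, section 11.2 says: "Analysis of variables will be conducted separately on each eye, and data will not be pooled".

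The text does not decide between them. On the single-lens reading (an assumption), power with 52 pairs depends strongly on the correlation:

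| r | d = 0.28/√(2(1 − r)) | Power, n = 52 |
|---|---|---|
| 0.5 | 0.280 | 51% |
| 0.6 | 0.313 | 60% |
| 0.7 | 0.361 | 72% |
| 0.75 | 0.396 | 80% |
| 0.8 | 0.443 | 88% |

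**Step 5: power at the completion target.** With 45 analysed pairs and 5/12.6, the noncentrality is 0.3968 × √45 = 2.662 against a critical value of 2.015, so power is 74.0%. With 45 pairs, 80% power is reached at d = 0.427, or 0.427 × 12.6 = 5.4 points on the 100-point scale.

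**The case against.** The strongest reply is that no arithmetic error is proved. Effect size is undefined, and 0.28 is 0.396 divided by √2, so it could be the same calculation on a single-lens SD with correlation 0.75, or a repeated-measures f with zero correlation. Repeated-measures ANOVA is the first test listed in Table 5. On either reading 0.28 agrees with n = 52, and deleting it outright would presume the answer. This stands as a limit on the finding: the origin of 0.28 cannot be settled. It does not rescue the text. The sentence names a paired t-test, states no other scale, and without its correlation a single-lens 0.28 could mean anything from 51% to 88% power over the range shown.

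On the completers, section 11.2 keeps every evaluated participant in the analysis, and someone who leaves after two periods may still supply one lens comparison. That also stands. Before any exclusion of data, a comparison could have between 45 and 52 pairs if the target is met at full enrolment, with power from 74% to 80%. Out-of-window exclusions, missing points or lower enrolment could take it lower, so 45 is a reference point and not a bound. At alpha 0.10, 45 pairs give 83.5% power, but section 11.2 sets significance at 0.05.

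Finally, section 11.1 works on a 100-point scale while the visit sections collect comfort on 0–10. Any added sentence should therefore name its scale.

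**Conclusion.** The concern holds, as a minor point. Read as a paired effect size, 0.28 does not follow from the inputs in its own sentence: 52 pairs detect 0.40, and at 0.28 they have 51% power. Under any other reading the figure is undefined. The 80% power for 5 points holds with 52 analysed pairs and falls to 74% with 45, which the plan does not say.

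These results assume that the 12.6 in Table 4 is the SD of within-participant differences, the reading under which the table reproduces. The sample size of 52 is correct for its inputs and rests on the 5-point target, not on 0.28. Design and analysis are unaffected.

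**What to change.** In section 11.1, replace the 0.28 statement with wording such as: *With 52 analysed pairs, the smallest standardised difference (mean difference divided by the SD of within-participant differences) detectable with 80% power at two-sided alpha 0.05 is 0.40.* If the sponsor can document another metric for 0.28, define it beside the 0.40, with the SD and correlation it uses.

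Add: *With 45 analysed pairs, power is 74% for a difference of 5 points on the 100-point scale (SD of differences 12.6); 80% power is reached at a standardised difference of 0.43 (5.4 points).*

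An optional clerical edit is to change confidence to power in the sentence on the 5-point difference.

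The cost is wording in section 11.1 only. The maximum of 52, the target of 45, the tests and alpha stay as they are. The stated sensitivity becomes less favourable.

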4.8.3 DISPENSING LENS PAIR #1

The participant will be assigned a randomization ID and the first pair (lens pair #1) of contact lenses (either test or one of the control lenses) will be selected according to the randomization table.

- Lens pair #1 will be provided to participants in a manner which does not unmask the participant, as described in Section 4.7.4.
- The lenses will be inserted by the participant.
- The contact lenses will be allowed to settle for 10 minutes.
- The participant will be asked to give subjective binocular ratings for:
 - Comfort at insertion (0-10 scale)
 - Ease of insertion (0-10 scale)
 - Speed of settling (0-10 scale)
 - Visual quality (0-10 scale)
 - Vision stability (0-10 scale)
 - Overall satisfaction (0-10 scale)
- Monocular and binocular logMAR visual acuity will be recorded with high contrast letters under high (300-600 lux) and low (1-5 lux) room illumination.
- Lens surface and fit will then be assessed and graded according to the CVI grading scales for the following:
 - Lens wettability (0-4 scale)
 - Centration (mm)
 - Post-blink movement (mm)
 - Toric mark visibility

- Lens orientation (3 measurements per lens)
 - Overall stability of toric mark position
 - Overall lens fit acceptance (0-4 scale)
- The participant will be given a set of daily subjective questionnaires (Appendix 12) to be completed at home on days 1, 3 and 6 starting the morning after the dispensing visit (day 0), to reflect their lens wear experience at the time of rating. Participant will be given careful explanation of how and when to complete them. Questions will include:
 - Time of lens insertion and removal
 - Comfort after insertion (i.e. after lens settling), after 4, 8, and 12 hours, and just before lens removal (0-10 scale)
 - Dryness after 4, 8, and 12 hours, and just before lens removal (0-10 scale)
 - Visual quality/clarity after insertion (i.e. after lens settling), after 4, 8, and 12 hours, and just before lens removal (0-10 scale)
 - Vision stability after insertion (i.e. after lens settling), after 4, 8, and 12 hours, and just before lens removal (0-10 scale)

The participant will be asked to wear the study lenses for at least 12 hours per day and 6 days per week.

- Participant will be provided with sufficient contact lens supply.
- The participant will be discharged and reminded to return for the 1-week visit of lens pair #1 and to bring back all lens package foils.

4.8.4 1-WEEK FOLLOW-UP OF PAIR #1 & DISPENSING PAIR #2

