Participants will be asked to wear lenses for at least 4 hours prior to the visit appointment. Participants who attend without lenses in-situ (wearing lenses) for at least four hours will be rescheduled.

- The participant will be asked to score their subjective responses by reflecting on a typical day during the previous week of lens wear, as detailed in the subjective ratings form (Appendix 11) and includes the following:
 - Wear time at this visit (hours)
 - Wear time per day during previous 1 week (hours)
 - Comfortable wear time per day during previous 1 week (hours)
 - Overall comfort (0-10 scale)

- Overall dryness (0-10 scale)
 - Ease of insertion (0-10 scale)
 - Ease of removal (0-10 scale)
 - Overall visual quality/clarity (0-10 scale)
 - Overall visual stability (0-10 scale)
 - Overall satisfaction (0-10 scale)
 - Comments by participants
- Monocular and binocular logMAR visual acuity will be recorded with high contrast letters under high and low room illumination.
 - Lens surface and fit will then be assessed and graded according to the CVI grading scales for the following:
 - Lens wettability (0-4 scale)
 - Centration (mm)
 - Post-blink movement (mm)
 - Toric mark visibility
 - Lens orientation (3 measurements per lens)
 - Overall stability of toric mark position
 - Overall lens fit acceptance (0-4 scale)
 - The lenses will be removed and retained. The disposal procedures are detailed in Section 4.7.6.
 - Slit lamp biomicroscopy will be assessed according to the CVI approved study biomicroscopy CRF.
 - There will be a 10 minute wash-out before insertion of lens pair #2.
 - Lens pair #2 will be provided to participants in a manner which does not unmask the participant, as described in Section 4.7.4.
 - The lenses will be inserted by the participant.
 - Procedures of fit and assessment will be repeated as detailed in the dispensing visit, section 4.8.3.
 - The participant will be discharged and reminded to return for the 1-week visit of lens pair #2 and to bring back all lens package foils.

4.8.5 1-WEEK FOLLOW-UP OF PAIR #2 & DISPENSING PAIR #3

Participants will be asked to wear lenses for at least 4 hours prior to the visit appointment. Participants who attend without lenses in-situ (wearing lenses) for at least four hours will be rescheduled.

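### Section 11.1 and Table 4 give the detectable comfort differences and SDs on a 100-point scale, but comfort is collected on 0-10 and no conversion is stated

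*Combined protocol and SAP*

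**What the plan says.** The sizing statement is in section 11.1. It caps enrolment ("The maximum sample size will be 52") and names the test: "For a two-sided paired t-test with an alpha of 0.05 and a power goal of 80" percent. It then expresses the result in rating points: "This sample size will give approximately 80% confidence to detect a difference of 5 points in comfort ratings". That sentence names no scale. The next paragraph does: it states "Assuming a standard deviation of 12.6 points, a sample size of 52 participants provides 80% power", and it puts the comfort difference to be found at "between 5 points on a 100-point scale". Table 4 has two rows, a difference of 5 with SD 12.6 and a difference of 7 with SD 17.6. Each needs 52 participants at alpha 0.05 and 41 at alpha 0.10.

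The procedures use a different scale. At each dispensing (section 4.8.3, repeated for pairs 2 and 3) the item is "Comfort at insertion (0-10 scale". The take-home questionnaire for days 1, 3 and 6 also rates comfort 0-10. At the three 1-week visits (sections 4.8.4 to 4.8.6) the item is "Overall comfort (0-10 scale". Dryness and visual quality, the other rated primary outcomes in section 2, are 0-10 as well. Outside section 11.1, the visible text mentions no 100-point instrument, no conversion and no SD for a 0-10 rating. It also does not say which comfort rating the calculation refers to.

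**The concern.** Comfort is the first primary outcome listed in section 2 and the only one used for sizing, so section 11.1 holds the trial's only stated detectable difference. Section 3 hypothesises that the test lens will do as well as or better than two controls, and the visible text gives no margin. A comfort result with no significant difference is therefore likely to be read against the detectable difference. That figure should be in the units of the data.

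The mismatch also leaves the SD unanchored. The source of 12.6 is not given, and nothing says it was observed on the instrument used here. Power depends on the ratio of difference to SD, so this is the part that could matter in practice.

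**Working it through.** **Inputs.** From section 11.1 and Table 4: two-sided paired t-test, alpha 0.05 (0.10 in the last column), power 80%, n = 52, difference 5 with SD 12.6, difference 7 with SD 17.6. From sections 4.8.3 to 4.8.6: comfort rated 0-10. Assumption: the SDs are those of the within-person difference. The plan's figures reproduce on that reading.

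**Method.** Standardised effect d = difference / SD; noncentrality = d × √n on n − 1 degrees of freedom. Power is the probability that a noncentral t variable falls beyond the two-sided critical value.

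**Step 1: reproduce Table 4.**
- 5 / 12.6 = 0.397. At n = 52 the noncentrality is 0.3968 × √52 = 2.862, the critical value is 2.008 and power is 80.2%. The smallest n reaching 80% is 52 at alpha 0.05 and 41 at alpha 0.10.
- 7 / 17.6 = 0.398. Power at n = 52 is 80.3%. The smallest n is again 52 and 41.

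All four cells match.

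**Step 2: can these inputs describe 0-10 ratings as they stand?** The difference between two 0-10 ratings lies between −10 and +10. The SD of a variable confined to a range cannot exceed half that range, here 20 / 2 = 10. Both 12.6 and 17.6 exceed 10, so neither can be an SD on the collected scale.

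**Step 3: convert.** The plan gives no conversion, so a plain factor of 10 is an assumption.
- 5 / 10 = 0.5 point and 12.6 / 10 = 1.26; d = 0.5 / 1.26 = 0.397.
- 7 / 10 = 0.7 point and 17.6 / 10 = 1.76; d = 0.7 / 1.76 = 0.398.

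The factor cancels in d, so n = 52 and 41 and power of 80.2% and 80.3% at n = 52 are unchanged. At n = 52 the difference detectable with 80% power is 0.396 × 1.26 = 0.50 point on 0-10, the counterpart of 0.396 × 12.6 = 4.99 on 0-100.

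**Step 4: how much depends on the SD?** The documents give no SD for the 0-10 scale, so the values other than 1.26 are an assumed range. All rows use n = 52 and two-sided alpha 0.05.

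| SD of difference (0-10) | d for 0.5 point | Power for 0.5 point | Difference detectable with 80% power |
|---|---|---|---|
| 1.0 | 0.500 | 94% | 0.40 |
| 1.26 (converted) | 0.397 | 80% | 0.50 |
| 1.5 | 0.333 | 65% | 0.59 |
| 2.0 | 0.250 | 42% | 0.79 |

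**The case against.** The best defence is that no arithmetic is wrong. Table 4 reproduces, and a paired t-test is indifferent to linear rescaling, so 52 and 80% survive any constant conversion factor. Section 11.1 also names its scale one paragraph after the bare figure of 5 points, so a careful reader will take the target as 5% of the scale range. All of this stands. It makes the point one of units and of the SD's provenance, not an error in the sample size.

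Three stronger readings are tempting, and the documents do not support them.

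- *The detectable difference is overstated tenfold, or is half of the rating scale.* This needs the first sentence to be read alone. The stated 100-point scale and an SD too large for 0-10 ratings both rule it out.
- *The sample size is wrong.* Nothing in the mismatch shows this; Step 3 gives the same number.
- *Power falls below 80% because 0-10 answers are whole numbers.* The rating forms (Appendices 11 and 12) are not in the text, so the response step is unknown. Table 5 lists analogue and numeric scales together among the continuous variables, which does not point to whole numbers. The source of 12.6 is also unstated. If it came from coarse ratings, it already contains the rounding, and adding more would count it twice.

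The defence does not supply the missing link. The plan never says how 0-10 ratings relate to the 100-point figures, or that the SD applies to them.

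**Conclusion.** The point holds as a mismatch of units. The differences and SDs in section 11.1 and Table 4 are on a scale on which the trial collects no comfort rating, and no conversion is given, so they do not describe the endpoint as collected. With a factor of 10 (assumed) the figures become 0.5 point with SD 1.26 and 0.7 point with SD 1.76. The sample size of 52 and the 80% power do not change.

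The residual uncertainty is the SD. Over an assumed range of 1.0 to 2.0, power for 0.5 point at n = 52 runs from about 94% to 42%. That range illustrates sensitivity; it is not evidence that 1.26 is wrong. The scale is taken from the procedure sections, since the rating forms themselves cannot be seen.

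**What to change.** Restate section 11.1 and Table 4 in units of the 0-10 ratings. If a factor of 10 is what was meant, the rows read 0.5 point with SD 1.26 and 0.7 point with SD 1.76, with 52 and 41 participants as now. If another conversion was meant, state it. Say which comfort rating the calculation refers to, give the source of the SD, and confirm that it is the SD of a within-person difference on the 0-10 instrument. If the confirmed SD differs, restate the detectable difference from it.

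The cost is a wording change, with no added participants, visits or procedures. A separate matter in the same section is best settled in the same edit: the stated effect size of 0.28 does not equal 5 / 12.6 = 0.397.

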3 HYPOTHESIS

The study hypothesis is that the MyDay toric test lens (MD-T) will perform as well or better clinically than the two control lenses: 1-Day Acuvue Moist for Astigmatism (1-DAM-T) and Dailies AquaComfort Plus Toric (DACP-T).

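### The 80% power in Section 11.1 is for one comparison with all 52 analysed: it is 74% at the targeted 45 completers, and lower again if the two-control hypothesis needs success against both

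*Combined protocol and SAP*

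**What the plan says.** Section 3 has one hypothesis: that MD-T "will perform as well or better clinically than the two control lenses", which are then named (1-DAM-T and DACP-T). It gives no margin and no rule for combining the two comparisons.

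Section 11.1 opens with "The maximum sample size will be 52" and sets the test: "For a two-sided paired t-test with an alpha of 0.05 and a power goal of 80" per cent. It continues "This sample size will give approximately 80% confidence to detect a difference of 5 points in comfort ratings", and describes its table thus: "Table 4 shows the sample size determination for a difference between two means in comfort scores". The variability is given as "Assuming a standard deviation of 12.6 points", and the conclusion is that "a sample size of 52 participants provides 80% power to detect a trend in difference of comfort scores". The section does not say which control is meant, and it does not mention power across two controls.

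Section 4.6.1 allows up to 52 participants to be randomized and aims for 45 completers. Section 11.2 uses everyone who was evaluated, drops missing data points without imputing them, and tests at 0.05 "with no adjustments for multiple comparisons".

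**The concern.** Someone reading Section 11.1 after Section 3 will take 80% as the power of the study. It is the power of one MD-T-versus-control test with the maximum number analysed. Two things separate that from the study as planned.

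- **Number analysed.** The plan expects about 45 people to finish all three lenses and does not impute. A figure that holds only at 52 overstates what the plan expects to have.
- **Two controls.** The most natural reading of Section 3 is that MD-T must meet the bar against each control. The chance of passing two tests is lower than the chance of passing one unless the two differences are almost perfectly correlated.

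At stake is the risk of a missed effect that the sponsor believes it has accepted, and how to read a result that succeeds against one control and not the other. The plan gives no reading for that result.

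**Working it through.** **Inputs from the plan.** Mean difference 5 points; SD of individual differences 12.6 (Table 4); paired t-test, two-sided 0.05, no multiplicity adjustment; n = 52 (Section 11.1) or 45 (Section 4.6.1). The standardised difference is 5/12.6 = 0.397. Section 11.1 also quotes a detectable effect size of 0.28. That does not match 5/12.6; it is a separate inconsistency and is not used here.

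**Step 1: reproduce the stated figure.** Power is P(|T| > t(0.975, n−1)), where T is noncentral t with n−1 degrees of freedom and noncentrality 0.397 × √n.

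- n = 52: noncentrality 2.86, critical value 2.008, power 80.2%.
- The smallest n reaching 80% is 52 at alpha 0.05 and 41 at alpha 0.10. The second row of Table 4 (7/17.6 = 0.398) gives the same two sizes.

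Table 4 is therefore correct for one comparison.

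**Step 2: the same comparison at 45.** Noncentrality 2.66, critical value 2.015, power 74.0%. This step needs no assumption beyond the plan's inputs.

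**Step 3: both comparisons.** Suppose success means significance in favour of MD-T against both controls, and the true difference is 5 from each. The two differences share the MD-T rating, so their correlation ρ is needed. The documents do not give it. If the SD of 12.6 holds for all three lens pairs, including control versus control, then

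12.6² = Var[(MD-T − control B) − (MD-T − control A)] = 2 × 12.6² × (1 − ρ), so ρ = 0.5.

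That is an assumption, so the range is shown. Joint power from 400,000 simulated pairs of correlated paired t-tests per case:

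| ρ | n = 52 | n = 45 |
|---|---|---|
| 0 | 64.4% | 54.8% |
| 0.5 | 68.8% | 60.7% |
| 0.75 | 72.0% | 64.6% |
| 0.9 | 75.1% | 68.1% |
| near 1 | about 80% | about 74% |

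**Step 4: separate the two causes (ρ = 0.5).** From 80.2% to 74.0% (6.2 points) comes from 45 rather than 52 analysed. From 74.0% to 60.7% (13.3 points) comes from requiring both controls.

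**Step 5: split results (ρ = 0.5).** The chance of success against exactly one control is 2 × (80.2 − 68.8) = about 23% at 52, and 2 × (74.0 − 60.7) = about 27% at 45.

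**Step 6: other readings of the hypothesis.** For a non-inferiority test with margin M and true difference D, the 5 in the noncentrality becomes D + M. All margins here are assumed; ρ = 0.5.

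| Reading | Joint power, n = 52 | Joint power, n = 45 |
|---|---|---|
| M = 5, D = 0, one-sided 0.025 | 69% | 61% |
| M = 5, D = 0, one-sided 0.05 | 80% | 74% |
| M = 2, D = 5, one-sided 0.025 | about 96% | about 92% |
| M = 5, D = 5, one-sided 0.025 | above 99% | above 99% |

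**The case against.** The strongest reply is that Section 11.1 contains no arithmetic error. It names a paired t-test and a difference between two means, so it is visibly about one pair of lenses, and it never says that 80% is the power for the whole hypothesis. The rule that both comparisons must succeed is inferred from the wording of Section 3, and the correlation is not in the documents. Moreover, the hypothesis is that MD-T is as good or better, not that it is 5 points better. Step 6 shows that under some non-inferiority readings the joint power is well above 80%. Finally, Section 11.2 analyses everyone evaluated, so a given comparison may include more than 45 people.

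Most of this stands, and it limits the point. A reader might infer that the study has about a one-in-three risk of failing on its own hypothesis. The documents do not support that: 69% belongs to one scenario, with an inferred rule, an assumed correlation and a true 5-point difference from each control. A reader might also infer that the plan's inputs alone give 69% and 61%. They do not; they give 80% and 74% per comparison. Nor is a split result the likely outcome, at about 23–27%.

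What the reply does not remove is that 80% stands unlabelled in a study with two named controls and a completer target below 52. The 74% needs none of the disputed assumptions. For any correlation short of 1, requiring both comparisons lowers power further in the scenario that Section 11.1 itself uses.

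**Conclusion.** The point holds as a labelling and disclosure fault, not a miscalculation. The 80% is correct for one MD-T-control comparison with 52 analysed. At the plan's target of 45 completers it is 74%, on the plan's inputs alone.

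If the hypothesis requires a significant 5-point comfort difference against both controls, power is about 69% at 52 and 61% at 45 with correlation 0.5. For correlation 0 to 0.9 it is 64–75% and 55–68%, reaching 80% and 74% only as the correlation nears 1. Part of the 61% is attrition rather than the second control.

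The joint figures apply to comfort only. They carry over to an as-good-as claim only under an assumed 5-point margin, true difference 0 and one-sided 0.025. Someone might conclude that the sample size must rise; that does not follow, because the plan has not said that both comparisons must succeed or that 80% is wanted jointly.

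**What to change.** In Section 11.1, replace the unqualified power statement with: *80% power is per MD-T-control comparison with 52 analysed (74% with the targeted 45). Power to show the 5-point difference against both controls is about 69% and 61%, assuming a correlation of 0.5 between the two differences (64–75% and 55–68% for correlation 0 to 0.9).*

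In Section 3, state whether the hypothesis requires both comparisons to succeed. If it does, a split result does not establish it, and no alpha adjustment is needed for that rule. If it does not, say how each comparison will be read on its own; the joint figures then become background.

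The cost is two or three sentences. There are no extra participants, visits or tests. The only drawback is a less favourable stated power.
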